8.4.3. Handling of Individual Warts that Combine Over the Course of the Study

For the endpoints associated with wart count, warts that combine could be problematic for analysis purposes. Should two warts combine into a single wart at a post baseline visit, the wart count would be reduced by 1 and the percent change reduction would be 50%. However, such calculations may not be representative of actual wart changes.

In the event two or more warts combine into a single wart, all information regarding the combined wart will be recorded on the wart with the first wart number sequentially. Warts other than the first wart that merged to create the combined wart will be marked as "Other, specify" on the Wart Location and Measurement CRF. The Other text field will begin with "WART COMBINED" to flag the wart as one that combined with other warts.

For endpoints that involve or are related to wart count, warts that combine at post baseline visits will be considered a single wart. In addition, for the complete clearance and change/percent change in number of warts endpoints, sensitivity analysis will be carried out where the number of warts that merged to create the combined wart will be imputed for all subsequent visits- as long as the combined wart does not clear.

8.5. Interim Analysis and Data Monitoring

No formal interim analysis or data monitoring is planned for this study.

8.6. Multiple Comparison/Multiplicity

No formal statistical comparisons are planned; thus, no adjustment for multiple comparisons is needed.

8.7. Examination of Subgroups

Analyses based on subgroups of interest may be carried out for exploratory purposes. Possible analyses include the following:

- Gender: Female, Male.
- Age: 12-17 years old, 18-45 years old, >45 years old
- Number of warts at baseline: 1-2 warts, >2 warts
- Fitzpatrick Skin Type: I or II, III or IV, V or VI
- Duration of warts: <1 year, 1-2 years, 3 to 5 years, >5 years. Duration of warts will be defined by comparing the date of informed consent to the date the warts were first self/parent identified. Partial dates will be imputed using the same procedure as used to calculate Time since Clinical Diagnosis. For details, see Section 7.3.

9. Methods of Efficacy Analysis

9.1. Complete Clearance of Treatable Warts

Counts and percent of subjects who have complete clearance of all treatable warts (baseline and new) will be displayed by visit. Complete clearance will be defined as no warts (treatable wart count=0) reported for a subject per the Wart Location and Measurement form. Number of common warts (treatable and untreatable) at unscheduled visits will be displayed in listings.

9.2. Change and Percent Change in Number of Warts

Number of warts present will be determined by the number of wart forms filled out with a wart diameter >0mm at each treatment visit as well as the EOT visit and 3 follow-up visits. For each post baseline treatment visit, the change in number of warts from baseline will be calculated. Summary statistics of number of warts will be displayed for each post baseline visit. Summary statistics of change in number of warts from baseline will also be displayed.

Percent change of warts will be calculated for each post baseline visit. Percent change will be calculated using the following formula (in formula below, warts refers to treatable warts):

$$\text{Percent (\%) Change} = \left(\frac{\text{Warts at Post Baseline Visit} - \text{Warts at Baseline Visit}}{\text{Warts at Baseline Visit}} \right) * 100$$

Analysis of percent change in number of warts will be carried out in the same manner as change in number of warts.

As described in Section 8.4.3, should any combined warts be reported, sensitivity analysis will be carried for change and percent change endpoints in which the number of warts which merge to create a combined wart will be imputed for all subsequent visits until the combined wart has cleared.

Section 8.4.2 specifies that the LOCF method will be used to impute result for visits with missing wart counts. This includes imputation of all treatment and follow up visits as well as the EOT visit. To investigate the potential impact the LOCF method could have on table summaries for change/percent change wart counts, an additional set of sensitivity analysis will be carried which only considers wart counts reported with no imputation. The analysis will be identical to the analysis described above, with the only difference being whether imputation is carried out or not.

9.3. Wart Percent (%) Reduction

At each treatment visit, the EOT visit and each follow-up visit, the number of warts will be reported. The percent change in number of warts will be calculated as described in

Section 9.2. Based on the percent reduction of warts, subjects will be assessed and assigned to one of 2 categories: $\geq 50\%$ reduction of warts, $<50\%$ reduction in warts. Subject counts and percentage of subjects for each of these categories will be displayed by treatment group and visit.

In addition, subjects will be assessed and assigned to one of 2 categories for each post baseline visit: Reduction of at least 1 treatment wart from Baseline, No Reduction of Warts from Baseline. Counts and percentages of each category will be presented by visit.

9.4. Reduction of Wart Area

At each treatment visit, the EOT visit and each follow-up visit, the maximum diameter of each wart will be measured. The area of each wart will be estimated assuming the shape of the wart is a circle. Thus, the area of each individual wart will be calculated using the formula:

$$\text{Area of Individual Wart} = \pi * \left(\frac{\text{Diameter of Individual Wart}}{2}\right)^2$$

Where π = the constant 3.14. At each treatment visit and the EOT visit, the total wart area will be determined for the subject by summing the areas of the individual warts estimated at that visit. The change and percent change in wart area will be calculated for each treatment visit and the EOT visit and will be summarized using summary statistics. The percent change will be calculated using the same formula described in Section 9.2 (using wart area rather than number of warts).

An additional set of analyses will include reporting the number and percent of subjects with a $\geq 50\%$ reduction in total wart area from baseline to the EOT visit. Subjects with a $\geq 50\%$ reduction from baseline in total wart area will be considered to have responded to treatment.

10. Safety Analysis

All safety analyses will be based on the Safety Population. For any by visit analyses to be carried out, visit windows discussed in Section 8 will be applied to safety data.

10.1. Extent of Exposure

The total number of warts treated will be collected by visit over the duration of the study. For each visit, the number of warts treated will be determined by taking the sum of warts reported on the Wart Assessment and New Wart Assessment forms, where the question “Was wart treated at this visit?” was marked Yes. Summary statistics of the number of warts treated over the duration of the study will be provided. Counts and percentages of number of treatment visits over the duration of the study will be generated. In addition, the total number of treatment visits and total number of warts treated across all subjects

will be displayed. A treatment visit will be defined as a visit in which at least one wart was reported to have been treated and/or treatment was administered.

10.2. Adverse Events

Adverse events summaries will only consider TEAEs. TEAEs are defined as those adverse events that occurred after dosing and those existing adverse events that worsened during the study. If it cannot be determined whether the adverse event is treatment emergent due to an incomplete (partial) onset date, the adverse event will be considered to be treatment emergent. Adverse events with an onset day after the EOS visit will be included in listings but not considered TEAEs; therefore, such adverse events will not be considered for table summaries. Verbatim terms entered into the clinical database via the EDC system will be mapped to preferred terms and system organ classes using version 20.0 of Medical Dictionary for Regulatory Activities (MedDRA).

Each adverse event summary will be displayed by treatment group. Summaries that are displayed by system organ class and preferred terms will be ordered by descending order of incidence of system organ class and preferred term within each system organ class. Summaries of the following types will be presented:

- Overall summary of the TEAEs which contain an overview of each item below.
- Subject count and incidence rate of TEAEs by MedDRA system organ class and preferred term.
- Subject count and incidence rate of TEAEs by MedDRA preferred term and highest severity. At each level of subject summarization, a subject is classified according to the highest severity if the subject reported one or more events.
- Subject count and incidence rate of TEAEs by MedDRA preferred term and closest relationship to study drug (Related/Not Related). Related AEs are those reported as “Definitely”, “Probable” or “Possibly”. At each level of subject summarization, a subject is classified according to the closest relationship if the subject reported one or more events. Adverse events with missing relationship will be considered related for this summary.
- Subject count and incidence rate of Serious TEAEs by MedDRA system organ class and preferred term.
- Subject count and incidence rate of TEAEs leading to withdrawal of study medication by MedDRA system organ class and preferred term.

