- b. Subjects are to be scheduled in 21-day intervals (+/- 4 days) after each treatment for subjects in Cohort 2. The next Treatment Visit is to be scheduled 21 (+/- 4 days) after the last treatment, but only after any LSR has resolved sufficiently to allow evaluation of the treatment site. The research team should be in contact with the patient until LSRs are resolved and a treatment visit can be scheduled within 21 days (+/- 4) when possible. The 24-hour phone contact may be conducted at +/- 6 hours. The 7-day phone contact may be conducted +/- 24 hrs.
- c. A final in person safety assessment, ERT, photos and study completion form will be completed at the Day 147 (EOS) Visit for all subjects. EOS conducted outside the Day 147 EOS visit window will be considered a protocol deviation. Treatments may be administered up to Day 75 in Cohort 2. Subjects in Cohort 2 are to attend all visits whether they have achieved complete clearance prior to and at the Day 84 (- 0/+ 8 days) EOT assessment.
- d. Demographics: date of birth, sex, race/ethnicity will be collected.
- e. Vital signs (e.g., temperature & heart rate) will be obtained at each treatment prior to application of Study drug. Height and weight will be collected at Screening/Day 1, EOT Day 84 (- 0/+ 8 days) and subsequent follow up visits Day 105, 126 and 147 (EOS).
- f. Limited physical examination. Symptom or AE-directed physical examination may be performed if warranted. (See Source/eCRF for a more detailed description)
- g. Dermatologic exam including Fitzpatrick Skin Type, location of each wart is identified and documented on the body map and source as outlined in the MOP. Measurements of warts should be recorded on Day 1 prior to treatment to confirm they meet inclusion criteria of ≤ 10 mm in diameter and ≤3 mm in height. Wart location, measurements and assessments are to be completed prior to each treatment application and/or each in-person visit. New warts should be recorded in the corresponding Source/eCRF. Instructions for measuring and documenting the and measurements are provided in the Manual of Operations.
- h. Paring at first visit by Dermatologist or qualified designee. Paring at additional treatment visits if significant hyperkeratosis or at Investigator’s discretion.

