AEs may include pre-treatment or post-treatment events that occur as a result of protocol-mandated procedures (e.g., invasive procedures, modification of the subject's previous therapeutic regimen). AEs should be captured even if they occur during periods without drug treatment or post-treatment periods. AE collection begins once the subject has signed informed consent and will continue until the EOS visit has been completed.

The investigator is responsible for performing periodic and special assessments for AEs. The investigator and study personnel will note all AEs mentioned by the subject starting from the day the informed consent is signed until the end of study visit (EOS; Day 84). All clinical complaints volunteered by or elicited from the subject or parent/guardian during the study will be recorded on the appropriate page of the source and eCRF for the study period indicated. The subject will receive appropriate treatment and medical supervision for any AE that occurs.

All unresolved AEs will be followed until the condition resolves and/or stabilize, the subject is lost to follow-up or 30-days after the end of study (EOS visit or up to 30 days after the EOS visit, whichever comes first.) All AEs will be summarized in the annual report or more frequently if requested by the regulatory agency. SAEs require special reporting in addition to documentation in the eCRF as described in Section 7.3.

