9.2.4 Safety Analysis

Safety analysis will be based on the safety population. Subjects will be assigned to the treatment received for any analysis of safety.

Adverse event data for the safety population will be listed individually, and the incidence of adverse events will be summarized by treatment, System Organ Class, and Preferred Term using frequency counts. LSRs will also be tracked by the incidence of subjects with each LSR and the maximal intensity throughout the study. These will be tabulated by total rate of occurrence and rate of severe occurrences. When calculating the incidence of adverse events, only Treatment Emergent Adverse Events (TEAEs) will be considered. In addition,

any adverse event with an onset date after the EOS visit will be considered off study and will not be included in tables summaries (though they will appear in adverse event listings). Each adverse event will be counted only once for a given subject. If the same adverse event occurs on multiple occasions for a subject, the occurrence with the highest severity and relationship to Study drug will be reported. If two or more adverse events are reported as a unit, the individual terms will be reported as separate events. Changes in vital signs, from baseline to the end of the study will be examined. Treatment-emergent changes from normal values to abnormal values will be identified as described in Section 4.3.1.

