10.3. Targeted Adverse Events- Local Skin Reactions

Local skin reactions (LSRs) to treatment reported by investigators and subjects will be recorded as adverse events. Two questions on the adverse event form are “Is this Adverse Event at a location where study drug was administered?” and “Did event occur during the paring procedure?” If the answer is Yes to the location question and No to the

paring procedure question, the adverse event will be considered a Local Skin Reaction. LSRs will be coded and summarized using similar methods as described in Section 10.2 for adverse events.

Summaries of LSRs will include the following:

- Subject count and incidence rate of LSRs by MedDRA system organ class and preferred term.
- Subject count and incidence rate of LSRs by MedDRA preferred term and highest severity. At each level of subject summarization, a subject is classified according to the highest severity if the subject reported one or more events.
- Subject count and incidence rate of LSRs by MedDRA preferred term and closest relationship to study drug (Related/Not Related). Related LSRs are those reported as “Definitely”, “Probably” or “Possibly”. At each level of subject summarization, a subject is classified according to the closest relationship if the subject reported one or more events. LSRs with missing relationship will be considered related for this summary.
- Subject count and incidence rate of serious LSRs by MedDRA system organ class and preferred term.
- Subject count and incidence rate of LSRs by study specific LSR categories. Mapping of LSRs will be done via a medical review. Possible categories of LSRs will include the following: Blistering, Pain, Pruritus, Erythema, Edema, Erosion/Ulceration, Flaking/Scaling/Dryness, Scabbing/Crusting, Pigmentation Changes.

Adverse events that appear at a location where drug was administered and occur during the paring procedure will not be considered LSRs. A separate summary table will be generated to summarize those adverse events that meet these conditions (i.e., the answer is Yes to the location question and Yes to the paring procedure question, therefore the adverse event will be considered as related to the paring procedure and not an LSR).

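### First-visit paring precedes the first dose, so the TEAE-only rule leaves its adverse events out of the general AE tables and possibly out of the paring table

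*SAP*

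**What the plan says.** SAP Section 10.2 sets the scope in one sentence: "Adverse events summaries will only consider TEAEs". It then defines the term: "TEAEs are defined as those adverse events that occurred after dosing and those existing adverse events that worsened during the study". One default favours inclusion: "If it cannot be determined whether the adverse event is treatment emergent due to an incomplete (partial) onset date", the event is counted as treatment-emergent. Protocol Section 9.2.4 has the same restriction, "When calculating the incidence of adverse events, only Treatment Emergent Adverse Events (TEAEs) will be considered", but does not define a TEAE.

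SAP Section 10.3 uses two questions on the AE form: whether the event is at a drug-treated location, and whether it happened during paring. Yes then No makes it a local skin reaction. Yes to both does not: "Adverse events that appear at a location where drug was administered and occur during the paring procedure will not be considered LSRs". Those Yes/Yes events go into a separate paring table.

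On what is collected, protocol Section 7.1 says "AEs may include pre-treatment or post-treatment events that occur as a result of protocol-mandated procedures", and collection starts at informed consent. On when paring happens, Table 2 footnote h says "Paring at first visit by Dermatologist or qualified designee" and makes paring at later treatment visits depend on significant hyperkeratosis or the investigator's discretion. Protocol Sections 4.1 and 6.2.2 apply paring only where it is needed, and always before application.

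**The concern.** Cohort 1 forbids paring and Cohort 2 allows it. It is done with a blade, and the protocol foresees bleeding and significant pain as reasons to stop. The SAP treats paring events as worth a table of their own.

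The rule that decides what is tabulated is tied to dosing, whereas paring comes before dosing. At the second and later treatment visits this does no harm, because a first dose has already been given. At the first visit it separates the event from the tables. That is also the visit for which footnote h mentions paring without a condition.

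Safety and tolerability of VP-102 is a primary Cohort 2 objective. A reader of the summary tables would take the paring rate as covering all parings, when it may cover only those after the first dose.

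**Working it through.** The plan states no figure to reproduce, so the check applies its rules to its visit sequence.

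**Order of events**
- Protocol Section 6.2.2: paring is item 10 and application is item 11 at Treatment Visit 1.
- Protocol Section 4.1 and SAP Section 3: paring removes scale before application.
- Inclusion criterion 3 and protocol Section 6.1: Cohort 2 warts may be pared before height is judged for eligibility. Screening may be up to 14 days before Day 1. Table 2 has no paring mark under Screening, so paring on an earlier day is permitted but not scheduled.

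**Step 1. TEAE rule in SAP Section 10.2, reading dosing as the first application**

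| Paring event | Treatment-emergent? | General AE tables |
|---|---|---|
| First paring, onset known to precede the dose, no worsening | No | Out; listings only |
| First paring, worsens after dosing | Yes | In |
| First paring, partial onset date leaves the order unknown | Yes, by default | In |
| First paring on the day of first dose, onset held as a date only | No rule stated | Undetermined |
| Eligibility paring on an earlier day, complete date, no worsening | No | Out; listings only |
| Paring at Treatment Visit 2 or later | Yes | In |

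For medications, SAP Section 10.8 places a start on the first-dose date explicitly on the concomitant side. Section 10.2 has no matching rule for adverse events.

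**Step 2. The two form answers in SAP Section 10.3**

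| At a drug-treated location? | During paring? | Result |
|---|---|---|
| Yes | No | Local skin reaction |
| Yes | Yes | Paring table |
| No | Yes | Neither |
| No | No | Neither |

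The third row matters because an event before the first application could be recorded as No for location: no drug had yet been put there.

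**Step 3. The two sections together.** The paring paragraph in Section 10.3 sets its two conditions, does not mention TEAE status, and claims no exemption from Section 10.2.
- If the general sentence governs, a first-paring event in the first or fifth row of Step 1 is out of the paring table.
- If Section 10.3 stands alone, the event is in when location is Yes and out when it is No.

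**Step 4. What can be counted.** Table 2 marks paring at five visits: the four treatment visits and EOT. The first visit is 1/5 = 20% of marked occasions, or 1/4 = 25% of treatment visits. For a subject pared only at the first visit it is 1/1 = 100%. These are shares of scheduled occasions, not of adverse events. The documents give no paring-event rate and no count of subjects who will need paring.

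**The case against.** The strongest reply is that Section 10.3 defines the paring table completely by two form answers. Its one reference back to Section 10.2 concerns local skin reactions, which these events are said not to be, and a specific definition can override a general sentence. On that reading the paring table keeps first-visit events. This stands as a possible reading, so loss from the paring table is not established. The SAP does not choose between the readings, and two programmers could build different tables from the same data.

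Second, the location question would often be answered Yes. Pared warts are normally treated at the same visit, partial treatment is not permitted, and the form may be completed afterwards. That is fair: a No is possible, not shown.

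Third, Section 10.2 speaks of onset date and onset day, never time. If only dates are held, same-day events might be counted. That would keep them by accident of data format, and it would not help a paring done on an earlier day.

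Fourth, the events remain in by-subject listings, which are readable at about 35 subjects. True: the loss is from summaries, not from the data. But a listing gives no incidence, and incidence is what a summary table is for.

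A reader might infer that a quarter to all of paring harm goes unreported. The documents do not support that. Such shares assume every subject is pared at the first visit, whereas protocol Section 6.2.2 says where applicable and Section 4.1 accepts that some warts need no paring. They also count sessions, not events. Nor does protocol Section 9.2.4 impose the after-dosing condition; that definition is in the SAP alone.

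**Conclusion.** The concern holds for the general AE tables, on the SAP's literal wording: a first-paring event with a complete onset date that places it before the dose, and with no later worsening, is collected but not tabulated. For the paring table, loss is possible but not certain. It turns on how Sections 10.2 and 10.3 are read together, how sites answer the location question, and whether onset is a date or a time.

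It would go too far to say that these events certainly drop out of both tables, or to attach a percentage of under-reporting. The size in events cannot be estimated from the documents. What can be said is that one of the five visits marked for paring is affected, together with any eligibility paring before it.

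The conclusion assumes that dosing in Section 10.2 means the first application. It is worth correcting because a stated rule excludes events that the SAP evidently meant to summarise, and the correction is small.

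**What to change.** **SAP Section 10.3.** Define the paring table as all adverse events in the Safety population with Yes to the paring question, regardless of TEAE status and of the location answer. Show events before the first dose separately from later ones. Use the Safety population as denominator, or subjects pared if paring is recorded per subject; the documents do not show such a record. List paring events in subjects who were pared but never dosed, since they fall outside the Safety population.

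**SAP Section 10.2.** Exempt this table from the TEAE-only restriction, and state how an event with onset on the day of first dose is classified. Because protocol Section 9.2.4 also limits incidence to TEAEs, note that the paring table is additional to those summaries.

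**Cost.** A few sentences and one selection condition, using a question already on the AE form. No study procedure changes. The reported paring-event rate may rise slightly. The change should precede database lock, since SAP Section 5 labels analyses added later as post hoc.
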